3.4.3 Pharmacodynamics and immunogenicity for ADA

Analyses to evaluate the pharmacokinetics and immunogenicity of MEDI4736 will be performed by AstraZeneca/MedImmune Clinical Pharmacology group or designee.

Immunogenicity results will be analysed descriptively by summarizing the number and percentage of patients who develop detectable anti-MEDI4736 antibodies. The immunogenicity titre will be reported for samples confirmed positive for the presence of anti-MEDI4736 antibodies. Summaries will be based upon all patients from the safety population who have at least one measurable ADA blood sample.

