1.3 Number of subjects

The original plan was to recruit approximately 350 subjects, stratified by current line of treatment (2nd/3rd line plus) and ethnicity (Asian/non-Asian), randomized in a 1:1 ratio to the treatments as specified below:

- AZD9291 80mg QD
- AZD9291 80mg QD and MEDI4736 10mg/kg q2w

The study was terminated early with only 29 patients randomized. This number is not considered sufficient for statistical comparison of the treatment groups, and all data reporting will be using summaries and listings.

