2.1.2 Safety Analysis Set

The Safety Analysis Set will consist of all subjects who received at least one dose of randomized treatment. Safety data will be summarized using the Safety Analysis Set, according to the treatment that patients received in their first cycle. Patients who received at least one dose of MEDI4736 in the first treatment cycle (15 +/-3 days) will be regarded as being in the combination treatment. Additional summaries might be provided for the patients who were randomised and received the combination but later discontinued MEDI4736 as appropriate.

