4.1 General principles

Continuous data will be summarized using descriptive statistics (number of observations, mean, standard deviation, median, 25th and 75th percentiles, minimum, and maximum). Frequencies and percentages will be used for summarizing categorical (discrete) data. Confidence intervals (CIs), when presented, will generally be 2-sided and constructed at the 95% level. For binomial variables, exact methods will be employed unless otherwise specified.

A month is operationally defined to be 30.4375 days.

For the primary summary, data will be presented in data listings by the randomized treatment group and subject number. All summaries will be presented by randomized treatment group unless otherwise specified.

For the final summary, data will be presented in data listings by Group A / Group B and subject number. All summaries will be presented by Group A / Group B unless otherwise specified.

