4.1.1 Baseline measurements and change from baseline variables

In general, for efficacy endpoints the last observed measurement prior to randomization will be considered the baseline measurement. For safety endpoints the last observation before the first dose of study treatment will be considered the baseline measurement unless otherwise specified. For assessments on the day of first dose where time is not captured, a nominal pre-dose indicator, if available, will serve as sufficient evidence that the assessment occurred prior to first dose.

Assessments on the day of the first dose where neither time nor a nominal pre-dose indicator are captured will be considered prior to the first dose if such procedures are required by the protocol to be conducted before the first dose.

In all summaries change from baseline variables will be calculated as the post-treatment value minus the value at baseline. The % change from baseline will be calculated as $(\text{post-baseline value} - \text{baseline value}) / \text{baseline value} \times 100$.

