4.3 PK, pharmacodynamics and immunogenicity summary

AZD9291, MEDI4736 and metabolites AZ5104 and AZ7550 PK concentrations will be summarised. AZD9291 and MEDI4736 concentrations will be plotted using box-blots. Individual concentrations and ratios of metabolites will be listed.

ADA concentrations will be summarised and listed.

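### The ADA incidence in SAP section 3.4.3 has an any-sample denominator that dilutes it, and no rule for patients already positive before MEDI4736

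*SAP*

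**What the plan says.** Section 3.4.3 of the SAP describes the immunogenicity result as "summarizing the number and percentage of patients who develop detectable anti-MEDI4736 antibodies". It then fixes who is counted: "Summaries will be based upon all patients from the safety population who have at least one measurable ADA blood sample". Titres are planned as well: "The immunogenicity titre will be reported for samples confirmed positive for the presence of anti-MEDI4736 antibodies".

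The parent population is defined in section 2.1.2: "The Safety Analysis Set will consist of all subjects who received at least one dose of randomized treatment". Table 1 in section 2.1.3 assigns ADA to this population, under a pharmacodynamics and immunogenicity heading that is separate from the safety data.

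Section 4.3 describes the output differently: "ADA concentrations will be summarised and listed".

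Two general rules bear on the point. Section 4.1.1 says "For safety endpoints the last observation before the first dose of study treatment will be considered the baseline measurement unless otherwise specified", and section 4.1 says "All summaries will be presented by randomized treatment group unless otherwise specified". Neither mentions ADA.

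**The concern.** To say that a patient developed antibodies, one needs a result before exposure and a result after it. The stated base asks for neither. This has two consequences, which act in opposite directions.

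- **Denominator.** A patient who gave a pre-dose sample and then left before any later sample meets the entry rule and can only be counted as not having developed antibodies. This lowers the percentage.
- **Numerator.** The word 'develop' suggests that treatment-emergent antibodies are meant, but no rule puts this into practice. Nothing says how to classify a patient who was positive before the first infusion, or a positive patient with no baseline sample. A programmer who counts any positive sample would not contradict the text, and would raise the percentage.

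In addition, sections 3.4.3 and 4.3 name different quantities. The first gives a yes/no status plus a titre in confirmed positives. The second names a concentration, which 3.4.3 does not produce.

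At stake is the main summary for the MEDI4736 immunogenicity objective in section 1.1. In an arm this small, the handling of one or two patients is visible in the result.

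**Working it through.** The SAP states no expected ADA rate, so there is no figure of its own to reproduce. The check sets the stated rule beside a paired-sample rule and shows how far they can differ.

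**Inputs**
- Randomised: 29 (section 1.3: "The study was terminated early with only 29 patients randomized").
- Allocation: 1:1 (section 1.3). The actual split is not given. 29/2 = 14.5, so N = 14 or 15 in the combination arm is assumed.
- T = patients with true treatment-emergent antibodies; P = patients positive before dosing, with no later rise, who are counted as developers; B = patients with only a baseline sample. The SAP gives none of these counts. The values used are illustrations: T = 0 or 1, P = 0 or 1, B = 0 or 3.

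**Formulas**
- Base as stated: (T + P)/N. Here P = 0 if 'develop' is read strictly, and P > 0 if any positive sample is counted.
- Paired-sample base: T/(N − B).

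**Dilution by baseline-only patients (T = 1, P = 0, B = 3)**
- N = 15: as stated 1/15 = 6.7%; paired 1/(15 − 3) = 1/12 = 8.3%. The difference is 8.33 − 6.67 = 1.67 percentage points.
- N = 14: as stated 1/14 = 7.1%; paired 1/(14 − 3) = 1/11 = 9.1%.
- In general, with P = 0, the stated rate is the paired rate multiplied by (N − B)/N, here 12/15 = 0.80 or 11/14 = 0.79.

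**Pre-existing antibodies counted as developed (T = 0, P = 1, B = 0)**
- N = 15: 1/15 = 6.7% instead of 0/15 = 0%.
- N = 14: 1/14 = 7.1% instead of 0/14 = 0%.
- Each patient classified this way adds 1/N, about 7 points.

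**Scale against sampling error.** Clopper-Pearson 95% intervals are 0.2 to 31.9% for 1/15, 0.2 to 38.5% for 1/12 and 0 to 21.8% for 0/15. The shifts are small beside these intervals. What is at issue is what the percentage means, not its precision.

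**Does another section close the gap?** Section 4.1.1 says which value serves as baseline for safety endpoints. It does not require a baseline ADA result, does not require a later one, and does not say how a baseline-positive patient is counted. Section 4.3 contains no classification by baseline status. Section 3.4.3 does not defer to the protocol on this point.

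**The case against.** The strongest reply is that 'develop' already carries the intended meaning: a patient who was positive before dosing and shows no rise has not developed antibodies. This is largely right. The SAP does not state a rule that counts pre-existing antibodies, and a reader who infers one goes too far. What remains is that no operational rule excludes them. The reply does not touch the denominator, which is stated outright.

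A second reply is that the protocol may define ADA status and sampling times. It may, and it is not at hand. But section 3.4.3 fixes the denominator itself, and a status definition elsewhere would not change that base.

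A third is that the endpoint is exploratory, in a study stopped at 29 patients with no hypothesis testing, and that a listing would let a reader check the percentage by hand. This stands, and it sets the priority.

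Three stronger readings are tempting but not supported:
- **Monotherapy patients dilute the rate.** The safety set covers both arms, but section 4.1 presents summaries by treatment group, and nothing says that AZD9291-only patients give ADA samples.
- **'Measurable' means positive, so the rate would be 100%.** Section 2.1.3 applies the word to a PK concentration; section 3.4.3 applies it to a blood sample and uses other words for positivity. The natural reading is a specimen that could be assayed.
- **This percentage is the only immunogenicity result.** Titres, and a summary and listing of ADA results, are also planned.

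**Conclusion.** The point holds as a minor one. Section 3.4.3 pairs an incidence with a base that admits patients in whom the incidence cannot be observed, and it leaves baseline-positive patients without a classification. Section 4.3 names a quantity that 3.4.3 does not produce.

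Under the assumed counts, the denominator rule moves 8.3% to 6.7% (N = 15) or 9.1% to 7.1% (N = 14). One pre-existing positive counted as a developer adds about 7 points. These sizes rest on an assumed arm of 14 or 15 and on assumed numbers of baseline-only and baseline-positive patients. If every treated patient has paired samples and none is positive at baseline, the two rules give the same result.

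The primary safety objective and the efficacy summaries are not affected.

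**What to change.** In section 3.4.3:
- Define an ADA-evaluable set: safety-set patients who received at least one dose of MEDI4736 and have a valid ADA result, positive or negative, at baseline and at least once after dosing. Base the incidence on this set.
- Report three quantities separately: positive at baseline; treatment-emergent (negative at baseline and positive later, or a pre-specified titre rise from a positive baseline); and positive at any time.
- List patients without paired samples.

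In section 4.3, replace the reference to ADA concentrations with ADA status and titre.

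The cost is a wording change and two further table rows, with a slightly smaller denominator. It should need no new sampling, provided a pre-dose ADA sample was taken. The SAP does not give the ADA sampling schedule, so this should be confirmed. If no pre-dose sample exists, treatment-emergent status cannot be established, and the result should be labelled as post-dose positivity instead.

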4. SUMMARY METHODS

All reporting of data will be descriptive, using summary tables and listings. No statistical hypothesis testing will be performed.

Due to the small numbers of patients, summaries will not be grouped by the stratification factors involved in the randomization.

4.1 General principles

Continuous data will be summarized using descriptive statistics (number of observations, mean, standard deviation, median, 25th and 75th percentiles, minimum, and maximum). Frequencies and percentages will be used for summarizing categorical (discrete) data. Confidence intervals (CIs), when presented, will generally be 2-sided and constructed at the 95% level. For binomial variables, exact methods will be employed unless otherwise specified.

A month is operationally defined to be 30.4375 days.

For the primary summary, data will be presented in data listings by the randomized treatment group and subject number. All summaries will be presented by randomized treatment group unless otherwise specified.

For the final summary, data will be presented in data listings by Group A / Group B and subject number. All summaries will be presented by Group A / Group B unless otherwise specified.

4.1.1 Baseline measurements and change from baseline variables

In general, for efficacy endpoints the last observed measurement prior to randomization will be considered the baseline measurement. For safety endpoints the last observation before the first dose of study treatment will be considered the baseline measurement unless otherwise specified. For assessments on the day of first dose where time is not captured, a nominal pre-dose indicator, if available, will serve as sufficient evidence that the assessment occurred prior to first dose.

Assessments on the day of the first dose where neither time nor a nominal pre-dose indicator are captured will be considered prior to the first dose if such procedures are required by the protocol to be conducted before the first dose.

In all summaries change from baseline variables will be calculated as the post-treatment value minus the value at baseline. The % change from baseline will be calculated as $(\text{post-baseline value} - \text{baseline value}) / \text{baseline value} \times 100$.

4.1.2 Study day definitions

For the purpose of efficacy data summary, Study Day 1 is defined as the date of randomization to study treatment. For visits (or events) that occur on or after randomization, study day is defined as $(\text{date of visit [event]} - \text{date of randomization} + 1)$. For visits (or events) that occur prior to randomization, study day is defined as $(\text{date of visit [event]} - \text{date of randomization})$. There is no Study Day 0.

For the purpose of safety data summary, Dose Day 1 is defined as the date of first dose of study treatment (referred to in the protocol as Week 1 Day 1). For visits (or events) that occur on or after first dose, dose day is defined as $(\text{date of visit [event]} - \text{date of first dose of study treatment} + 1)$. For visits (or events) that occur prior to first dose, dose day is defined as $(\text{date of visit [event]} - \text{date of first dose of study treatment})$. There is no Dose Day 0.

For listings (such as for AEs) that include the derivation of “days since last dose,” this is defined as $(\text{event date} - \text{date of last dose})$. Events that occur on the same day as the last dose of study drug will therefore be described as occurring zero days from the last dose of study drug.

4.1.3 Visit windows

For summaries of vital signs, laboratory data, ECG and target lesion size, assessments will be assigned to calculated visit windows (using study day).

The time windows should be exhaustive so that data recorded at any time point have the potential to be summarized. Inclusion within the visit window should be based on the actual date and not the intended date of the visit. For summaries at a subject level, all values should be included, regardless of whether they appear in a corresponding visit-based summary, when deriving a subject level statistic such as a maximum.

The window for the visits following baseline (including unscheduled visits) will be constructed in such a way that the upper limit of the interval falls half way between the two visits.

For summaries showing the maximum or minimum values, the maximum/minimum value recorded on treatment will be used (regardless of where it falls in an interval). Listings should display all values contributing to a time point for a subject; they should also highlight the value for that subject that was used in the summary table, wherever feasible.

For visit based summaries:

- If there is more than one value per subject within a visit window then the closest to the planned study day value should be summarized, or the earlier in the event the values are equidistant from the planned study day. The visit will be missing if no assessment was reported within the specified visit window around the planned study day.
- To prevent very large tables or plots being produced that contain many cells with meaningless data, summary statistics will be presented where at least 10 subjects in either treatment group have data recorded at a particular visit.

4.1.4 Handling missing data

In general, other than for partial dates, missing data will not be imputed and will be treated as missing.

4.1.4.1 Imputation of partial dates

Initial diagnosis date:

- If year is missing (or completely missing), do not impute.
- If only day is missing, impute day as 15th of the month.
- If day and month are missing, impute as July 1st.

Concomitant medication start date

- If year is missing (or completely missing), do not impute.
- If (year is present and month and day are missing) or (year and day are present and month is missing), impute as January 1st.
- If year and month are present and day is missing, impute day as first day of the month.

Concomitant medication end date

- If year is missing (or completely missing), do not impute.
- If (year is present and month and day are missing) or (year and day are present and month is missing), impute as December 31st.
- If year and month are present and day is missing, impute day as last day of the month.

4.1.5 Imputation rules for lab values outside of quantification range

Lab values below the lower limit of quantification (LLoQ) that are reported as “<LLoQ” or “≤LLoQ” in the database will be imputed by LLoQ x 0.99 for reporting purposes. The original value will be listed.

Lab values above the upper level of quantification (ULoQ) that are reported as “>ULoQ” or “≥ULoQ” in the database will be imputed by ULoQ x 1.01 for reporting purposes. The original value will be listed.

4.1.6 Rounding rules for reported percentages

For percentages $\geq 10\%$:

- Values $\geq X.5$ or above round to $X+1$.
- Values $>X$ but $<X.5$ round to X .

For percentages $< 10\%$:

- Values $\geq X.Y5$ or above round to $X.Y+0.1$.
- Values $>X.Y$ but $<X.Y5$ round to $X.Y$.

4.2 Summary methods

4.2.1 Subject disposition and data sets analyzed

Subject disposition will be listed and summarized for all patients. Summaries will include the number and percentage of subjects:

- Randomized

- Treated
- Subjects ongoing study treatment at the data cut-off
- Included in each analysis set (FAS, Safety, and PK)

In addition, the number and percentage of subjects who discontinued treatment and who discontinued the study, including a breakdown of the main reason for discontinuation will be presented for all subjects.

4.2.2 Protocol deviations

All important protocol deviations will be listed. All protocol deviations will be defined by the study team and identified before database lock.

4.2.3 Demographic and other baseline characteristics

Demographic and baseline subject characteristics will be listed and summarized for the Safety Analysis Set. Standard descriptive statistics will be presented for the continuous variables of:

- Age (years).
- Weight (kg).
- Height (cm).
- Body mass index (kg/m²) (calculated as $[\text{weight}/\text{height}^2]$ where weight is in kg and height is in m).

The total counts and percentages of subjects will be presented for the categorical variables of:

- Age group (years) (grouped as <50, ≥ 50 to <65, ≥ 65 to <75 and ≥ 75).
- Sex.
- Race.
- Ethnicity.
- Overall disease classification (metastatic, locally advanced, both).
- Site of disease.
- Baseline TL size (mean and categories: <40, 40-79, 80-119, and ≥ 120 mm).
- Histology.
- Smoking status.

- WHO performance status (0/1).

Receptor status at baseline will be summarised.

4.2.4 Medical history

Disease related medical history and relevant surgical history will be coded using MedDRA. All disease related medical and surgical history will be listed.

4.2.5 Anti-cancer medications and radiotherapy (prior, during, post-treatment with investigational product)

Medications received prior to, concomitantly, or post-treatment will be coded using the AstraZeneca Drug Dictionary Anatomical Therapeutic Chemical (ATC) Classification codes. Concomitant medications/radiotherapy will be listed and summarized for the Safety Analysis Set by ATC classification codes.

For the purpose of inclusion in prior and/or concomitant medication or therapy summaries, incomplete medication or radiotherapy start and stop dates will be imputed as detailed in Section 4.1.5.1.

Prior medications, concomitant and post-treatment medications are defined based on imputed start and stop dates as follows:

- Prior medications are those taken prior to screening with a stop date prior to the first dose of study treatment.
- Concomitant medications are those with a stop date on or after the first dose date of study treatment (and could have started prior to or during treatment).
- Post-treatment medications are those with a start date after the last dose date of study treatment.

EGFR-TKI therapies will be defined as approved EGFR-TKI therapies and will include gefitinib, erlotinib and afatinib.

4.2.5.1 Anti-cancer therapy

All anti-cancer therapies at baseline and post discontinuation will be summarized for the Safety Analysis Set. The number of anti-cancer therapy regimens and number of cycles will be summarized using descriptive statistics. The anti-cancer therapy agent, therapy class, best response, and treatment status will be summarized using frequencies and percentages. Any anti-cancer therapies will also be listed.

4.2.5.2 Radiotherapy

All radiotherapies will be summarized for the Safety Analysis Set. Any radiotherapy will also be listed.

4.2.6 Exposure

Exposure will be listed and summarized for Safety Analysis Set. The following summaries will be produced:

- Summary of duration of exposure of AZD9291
- Summary of duration of exposure of MEDI4736
- Summary of duration of treatment for each arm
- RDI and PID of AZD9291
- RDI and PID of MEDI4736
- Summary of interruptions and reductions of AZD9291
- Summary of interruptions and delays of MEDI4736

4.2.7 Efficacy

All efficacy summaries will be produced using the FAS.

4.2.7.1 Progression free survival landmark summary

Progression status assessed by investigator at time of landmark summary (at Month 6 and Month 12 from the last subject first dose) will be summarised.

Kaplan-Meier plots and estimates will be produced at time of landmark summary along with other descriptive summaries based on the FAS.

4.2.7.2 Sensitivity summary

The following sensitivity summary will be conducted:

(a) With confirmation of progression: RECIST 1.1 criteria will be used to assess PFS with the requirement for confirmation of progression (by investigator). Progressions will only be used in the summary where there is a scan no earlier than 4 weeks later that documents progression or where there is no following scan. The first scan documenting radiological progression will be used regardless.

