3. PRIMARY AND EXPLORATORY VARIABLES

3.1 Derivation of RECIST visit responses

All RECIST assessments, whether scheduled or unscheduled, will be included in the calculations. This is also regardless of whether a patient discontinues study drug.

For all patients, the RECIST version 1.1 (see further Appendix C of the CSP) tumour response data will be used to determine each patient's visit response. It will also be used to determine if and when a patient has progressed and also their best overall response.

The baseline tumour assessment is part of the screening procedures and should be performed within 28 days before the start of study treatment.

Prior to approval of CSP version 2.0, efficacy for all patients will be assessed by objective tumour assessments every 8 weeks (relative to the first dose) for the first 48 weeks, then every 12 weeks thereafter, until confirmed objective disease progression as defined by RECIST 1.1 (irrespective of the reason for stopping study drug and/or subsequent therapy). For patients who discontinue study drug due to toxicity or a reason other than confirmed progression of disease (PD), objective tumour assessments should be continued every 8 weeks for 48 weeks (relative to first dose) then every 12 weeks thereafter until confirmed objective disease

progression. If an unscheduled assessment is performed, and the patient has not progressed, every attempt should be made to perform the subsequent assessments at their scheduled visits. Patients on monotherapy AZD9291 will be assessed according to local practice until objective disease progression.

Disease progression requires confirmation, the confirmatory scan should occur preferably at the next scheduled visit and no earlier than 4 weeks after the initial assessment of PD in the absence of clinically significant deterioration. Study treatment will continue between the initial assessment of progression and confirmation for progression.

Progression would be considered confirmed if the following criteria are met:

- $\geq 20\%$ increase in the sum diameters of target lesions (TLs) compared with the nadir at 2 consecutive visits with an absolute increase of at least 5 mm.

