Note: For TLs, only the latest scan date is recorded out of all scans performed at that assessment for the TLs and similarly for NTLs only the latest scan date is recorded out of all scans performed at that assessment for the NTLs. Additionally, PFS will be obtained using the algorithm described above for the RECIST site investigator tumour data. An additional sensitivity summary using a modified version of the algorithm will be used, whereby any objective disease progression must be **confirmed by** the next scheduled scan. The **confirmatory** scan must be no sooner than 4 weeks after the initial suspected progression. If disease progression is **confirmed** (or disease progression occurs and no further scans are recorded) then the date of progression will be when it was originally observed. Patients with a single disease progression and no further tumour assessment scans will be treated as PD in the summary.

The proportion of patients alive and progression free at 6 months (i.e., APF6) will be defined as the Kaplan-Meier (KM) estimate of PFS at 6 months.

The proportion of patients alive and progression free at 12 months (i.e., APF12) will be defined as the KM estimate of PFS at 12 months.

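### For the confirmed-progression PFS summary, SAP 3.2.1 wants confirmation at the next scheduled scan but 4.2.7.2 accepts any scan at least 4 weeks later, so an unconfirmed PD that recurs later is handled differently

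*SAP*

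**What the plan says.** Both sections describe the same summary: investigator-assessed PFS by RECIST 1.1 with confirmation of progression required.

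- **SAP 3.2.1 (derivation).** It requires that "any objective disease progression must be confirmed by the next scheduled scan", and the confirming "scan must be no sooner than 4 weeks after the initial suspected progression". The one exception is that "Patients with a single disease progression and no further tumour assessment scans will be treated as PD in the summary". A confirmed progression is dated when it was first observed.
- **SAP 4.2.7.2 (summary methods).** The rule reads: "Progressions will only be used in the summary where there is a scan no earlier than 4 weeks later that documents progression", or where no scan follows. The section then adds: "The first scan documenting radiological progression will be used regardless". It limits confirmation neither to the next scan nor to a scheduled one.
- **SAP 3.1 (RECIST visit responses).** On conduct, "the confirmatory scan should occur preferably at the next scheduled visit and no earlier than 4 weeks after the initial assessment of PD", which is a preference. For target lesions, the criterion is a 20% increase "compared with the nadir at 2 consecutive visits with an absolute increase of at least 5 mm". The sentence on the sensitivity summary gives only a 28-day minimum. The same section includes unscheduled assessments in the calculations.

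**The concern.** A sensitivity summary that requires confirmation is meant to set aside a first PD that the following scan does not bear out. Under 3.2.1 it does so. Under 4.2.7.2, read literally, such a PD is readmitted and dated back to its first appearance whenever some later scan shows progression, even if one or more scans in between did not. That moves the confirmed result towards the unconfirmed one in exactly the patients for whom the two should differ. If such a patient exists, two programmers working from different sections would produce different Kaplan-Meier curves, and both could say that they followed the SAP.

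**Working it through.** The SAP gives no figure to reproduce here. The check is to apply both rules literally to the same scan histories.

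**Inputs**
- Scans every 8 weeks to week 48 (3.2.1). Every later scheduled scan therefore meets the 4-week minimum, and only the next-scan condition separates the rules.
- PFS time = event date − randomisation date + 1 (3.2.1). With first dose on the day of randomisation (assumed) and scans on schedule, a scan at week w falls on day 7w + 1: week 8 = 57, week 16 = 113, week 24 = 169, week 32 = 225.
- One month is 30.4375 days (4.1), so 6 months = 6 × 30.4375 = 182.6 days.
- 29 patients randomised 1:1 (1.3). Arm sizes are not stated; 14 and 15 are assumed.

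**Rules side by side.** Section 3.2.1 is taken to re-test each later PD on its own date, which it does not state outright. The last scan shown is the patient's last.

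| Scan history | 4.2.7.2 | 3.2.1 | Difference |
|---|---|---|---|
| PD wk 8, PD wk 16 | day 57 | day 57 | none |
| PD wk 8, non-PD wk 16, no PD later | no event | no event | none |
| PD wk 8, non-PD wk 16, PD wk 24 | day 57 | day 169 | date only: 112 days, both before day 182.6 |
| PD wk 16, non-PD wk 24, PD wk 32 | day 113 | day 225 | date: 112 days, either side of day 182.6 |
| PD wk 8, non-PD wk 16, PD wk 24, non-PD wk 32 | day 57 | no event | event status |

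**All patterns.** There are 2 + 4 + 8 + 16 + 32 + 64 = 126 PD/non-PD sequences of one to six eight-weekly scans.
- In 57 of them the first PD is followed by a non-PD scan.
- In 15 of those 57, PD is never seen again and neither rule gives an event.
- In the other 42, 4.2.7.2 counts the first PD and 3.2.1 does not. With re-testing, event status differs in 11 and only the date differs in 31 (11 + 31 = 42). Without re-testing, 3.2.1 gives no event in any of the 42.

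These are counts of possible patterns, not probabilities.

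**Size per patient.** With no censoring before 6 months, one patient moved across the landmark changes the 6-month Kaplan-Meier estimate (APF6) by 1/15 = 6.7 to 1/14 = 7.1 percentage points.

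**Unscheduled scans.** An unscheduled scan at least 4 weeks after the first PD could confirm it under 4.2.7.2, but not under a literal reading of 3.2.1.

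**The case against.** The best defence is that 3.2.1 is the full derivation and 4.2.7.2 a short restatement of it. The alternative in 4.2.7.2 for patients with no following scan hints that the following scan is the one to be tested. This is a plausible reading, but the SAP does not state it, and 4.2.7.2 as worded contains no such limit.

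Four stronger readings are tempting, and the document does not support them:

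- A reader might infer that every first PD not confirmed at the next scan is an event under 4.2.7.2. It is not: a later scan must again document progression.
- A reader might take 3.1 to require the next scan throughout. It states only a preference for the next scheduled visit. The consecutive-visit condition stands in the target-lesion criterion alone, not in those for non-target or new lesions.
- A reader might treat the sentence that ends in "The first scan documenting radiological progression will be used regardless" as a further contradiction. On dating, the two sections agree: a confirmed progression takes the date of its first appearance. The trouble is the missing next-scan condition in the sentence before it.
- A reader might quote a larger shift. With two non-PD scans between (PD at week 8, PD again at week 32) the gap is 225 − 57 = 168 days, but that is one chosen pattern.

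It also stands that opportunity is limited. After protocol version 2.0, Group A has no tumour scans, and confirmation is required only for Group B patients who stay on MEDI4736 after progression. The pattern would arise mainly from earlier follow-up.

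**Conclusion.** The inconsistency is real but minor. The sections give different confirmation rules for the same summary, and they diverge when a first PD is not confirmed at the next scan and PD recurs on a later one. The effect is then a change of date or of event status, depending on the pattern, and it may or may not cross the 6-month landmark. The dates in the examples rest on on-schedule scans, re-testing of later PDs under 3.2.1, and a final PD that is confirmed or is the last scan. The figure of about 7 points per patient also rests on a near-even split and no early censoring.

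The SAP gives no frequency for such patients, and there may be none. Efficacy is exploratory, nothing is tested, and PFS without confirmation is primary for efficacy reporting. No main result or safety conclusion depends on this point.

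**What to change.** Align 4.2.7.2 with 3.2.1, for example:

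> A progression counts only if the next scheduled scan, at least 4 weeks later, also shows progression, or if there is no further scan. If that scan does not show progression, the PD is disregarded and any later PD is tested for confirmation on its own date. A scan earlier than 4 weeks neither confirms nor refutes.

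Keep the dating sentence, but limit it to the first PD of the confirmed pair, or to the single PD with no further scan. State as well whether a PD whose only later scan falls within 4 weeks is handled as having no further scan, and whether an unscheduled scan at least 4 weeks later may stand in for the scheduled one.

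This changes the analysis rule only. It needs SAP wording and matching programming, with no extra scans, data or patients.
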